#### Cycle delay

After completion of each 21-day cycle, the start of a new cycle could be delayed for up to one 1 week (7 days) in cases of toxicity necessitating a dose delay. A subject whose cycle is delayed should be assessed within a week for resolution or recovery of toxicity and a decision regarding further delay.

There is no limit on the number of cycle delays that each subject may experience, as long as delays do not exceed one week or 28 days from the beginning of a cycle.

The following parameters must be met on the first day of a new cycle (after cycle 1):

- Platelet count  $\geq 50 \times 10^9/L$
- ANC  $\geq 1.0 \times 10^9/L$
- Non-hematologic toxicity of  $\geq$  grade 3 must have recovered to baseline or Grade  $\leq 1$

For severe hematologic toxicity (grade  $\geq 3$ ), laboratory evaluations may be repeated more frequently as necessary until the retreatment requirements are met. In the event of severe renal toxicity or hepatotoxicity, laboratory tests may be repeated more frequently as necessary until the toxicity resolves.

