**APPENDIX 1. SCHEDULE OF ASSESSMENTS**

Parameter	Pre-treatment Period Screening	Open-Label Treatment Period			Follow-Up a
In Clinic	Up to 28 days before enrollment	Cycle 1, Day 1 Cycles 2 to 3 (Day 1, + 7 or - 3 days)	Response Evaluation Cycle 2	End of Treatment Visit a (14 – 28 days after last dose of study drug)	Every 12 weeks (+ or - 1 week) for 52 weeks
Screening/Administrative					
Informed Consent	X				
Demographics/ Medical History	X				
Inclusion/Exclusion	X				
Staging and sAAPI	X				
Patient diary will be provided	X b				
Check patient medication diary for treatment compliance		X			
Study Drug Administration					
Acalabrutinib administration		Refer to Dose and Administration – Section 3.5.3			
R-ICE administration		Refer to Dose and Administration – Section 3.5.3			
Safety Assessments					
Complete physical examination	X k				
Directed physical examination with lymphoma symptoms reviewed and recorded b		X b, l		X	
Performance status (ECOG)	X k	X		X	
Vital Signs (heart rate, temperature, BP)	X k	X		X	
Weight	X k	X		X	
Height	X k				
BSA		X			
ECG	X			X	
Echocardiogram/MUGA scan c	X				
Concomitant Medications		←	X	→	
Adverse Events		←	X	→	X
Clinical Laboratory Assessments					
Hematology (CBC with differential: WBC, HGB, HCT, platelet count, ANC, ALC)	X k	X e		X	
Chemistry (albumin, ALP, ALT, AST, CO 2 , BUN, Ca, Cl, creatinine, glucose, LDH, Mg, phosphate/phosphorus, K, Na, total bilirubin, total protein, uric acid) d	X k	X f		X	
Chemistry (K)		X l			
Urinalysis		X l			
Coagulation panel (PT, aPTT, INR)	X				
HBV surface antigen and HCV (antibodies)	X				
Serum or urine β-HCG pregnancy test (for females with childbearing potential)	X e			X	
Total cell count, B cell count	X			X	

Parameter	Pretreatment Period Screening	Open-Label Treatment Period			Follow-Up n
In Clinic	Up to 28 days before enrollment	Cycles 1 to 3 (Day 1)	Response Evaluation Cycle 2	End of Treatment Visit a	
Efficacy Assessments					
CT imaging (neck, chest, abdomen, and pelvis) with IV or oral contrast	X h		X h	X i	
Whole body FDG-PET scan b, i	X h			X i	
Evaluation of other sites of disease b, i	X			X	

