Bone marrow biopsy j	X				
ctDNA assessment m	X			X	
Survival					X

ALC=absolute lymphocyte count; ALP=alkaline phosphatase; ALT=alanine aminotransferase; ANC=absolute neutrophil count; AP=alkaline phosphatase; aPTT= activated partial thromboplastin time; AST=aspartate aminotransferase;  $\beta$ -HCG=beta-human chorionic gonadotropin; BP=blood pressure; BSA=body surface area; BUN=blood urea nitrogen; Ca=calcium; Cl=chloride; CO2=bicarbonate; CT=computed tomography; ctDNA= circulating tumor DNA; ECG=electrocardiogram; ECOG=Eastern Cooperative Oncology Group; FDG=fluorodeoxyglucose; HBV=hepatitis B virus; HCV=hepatitis C virus; IHC=immunohistochemistry; INR= international normalized ratio; IV=intravenous; K=potassium; LDH=lactate dehydrogenase; Mg=magnesium; MUGA=multiple-gated acquisition scan; Na=sodium; PD=progressive disease; PET=positron emission tomography; PK=pharmacokinetics; PT=prothrombin time; R-ICE=rituximab, ifosfamide, carboplatin, and etoposide; SAAIPI= age-adjusted international prognostic index at the initiation of second-line therapy; WBC=white blood count.

a	This visit is required for all subjects. It should take place 14-28 days after the last dose of study drug.
b	Directed physical examination includes all organ systems that were previously abnormal or involved with disease and documentation of any clinically relevant abnormalities in any organ. Lymphoma symptoms reported at screening should be reviewed and recorded during the directed physical examination. Subjects should be questioned regarding changes in ocular status and referred to an ophthalmologist for a formal exam if any positive findings (Grade $\geq 2$ ) are reported.
c	Echocardiography or MUGA scan is mandatory at baseline; thereafter it can be repeated optionally at any time during the study if clinically relevant, or in case of cardiac adverse events, using the same modality as at baseline.
d	Calculated creatinine clearance of $\geq 60$ mL/minute/1.73 m  within 14 days before enrollment.
e	Samples can be taken on the day of or day prior to dosing, provided that results are available before the dose of study drug is given. Hematology should be done on Days 1, between Days 7 and 10, and on Day 14 of each cycle with a window of $\pm 1$ day. For pregnancy tests, if the pregnancy test during screening is within 28 days of Cycle 1 Day 1, it does not need to be repeated.

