f	Samples can be taken on the day of or day prior to dosing. The results do not need to be available before the dose of study drug is given.
g	Computed tomography and PET scans obtained for standard subject evaluations before signing ICF can be used for screening, but should not be older than 28 days prior to enrollment.
h	Computed tomography scan and PET scans will be performed at screening and at the end of Cycle 3. CT scan will occur Day 15-21 of Cycle 2 to demonstrate lack of progression of disease (PD)  . If PD, patient will be removed from study. Positron emission tomography scans must be done between Days 15 to 21 of Cycle 3.
i	Computed tomography and PET scans are required at early withdrawal. Computed tomography and PET scans performed after Cycle 3 are considered the End-of-Treatment disease efficacy assessment (or earlier if $< 3$ cycles administered as per investigator discretion). If early withdrawal prior to the end of Cycle 3, CT and PET scans are to be repeated.
j	Morphological and IHC examination of the bone marrow is required and should be performed within 28 days prior to the first dose of study drug. In subjects with bone marrow involvement prior to treatment, bone marrow biopsy must be repeated once during the study for confirmation of CR (preferentially within 30 days of initial documentation of CR). Bone marrow obtained for standard subject evaluations before signing ICF can be used for screening, but should not be older than 28 days prior to treatment.
k	If this visit occurs within 7 days of Cycle 1 Day 1. It may be used for the screening and Cycle 1 Day 1 treatment evaluations.
l	A directed physical exam, chemistry (potassium) and urinalysis assessments will be performed every day while participants are receiving R-ICE treatment.
m	RNB for patients with evaluable clonotype determined on pretreatment tumor specimen. Required ctDNA assessment time points: pre-treatment, and at EOT.
n	Follow-up every 12 weeks for 52 weeks after EOT visit, until removal from study, or until death. SAEs considered related to study drug should be documented
o	A patient diary will be provided to participants and study team members will advise participants on how to record information in the diary.

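### Footnote f lets Cycles 2 and 3 start before Day 1 chemistry results are known, although Section 3.8 makes recovery from Grade 3 or higher non-hematologic toxicity a condition for starting them

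*Combined protocol and SAP*

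**What the plan says.** Section 3.8, Cycle delay, lists conditions for re-treatment under the words "The following parameters must be met on the first day of a new cycle (after cycle 1"). Two are hematologic: platelets and ANC. The third is that a non-hematologic toxicity of Grade 3 or higher "must have recovered to baseline or Grade" 1 or lower.

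Appendix 1 schedules the tests that would show whether these conditions are met, but treats the two kinds of test differently.

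- Hematology (footnote e) may be sampled on the dosing day or the day before, "provided that results are available before the dose of study drug is given". It is also repeated within the cycle: "Hematology should be done on Days 1, between Days 7 and 10, and on Day 14 of each cycle".
- The full chemistry panel (footnote f) has the same sampling window, but "The results do not need to be available before the dose of study drug is given". Footnote f does not say that a same-day sample must be taken before the dose.

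Of the chemistry analytes, only potassium is tested again on schedule within a cycle, on R-ICE days (footnote l). Footnote k lets a screening visit within 7 days of Cycle 1 Day 1 stand in for that day's evaluations: "It may be used for the screening and Cycle 1 Day 1 treatment evaluations".

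**The concern.** A mandatory dosing condition is paired with an explicit permission not to know the result needed to apply it. The platelet and ANC conditions must be verifiable before the dose. The laboratory part of the non-hematologic condition need not be. Under the schedule, Cycle 2 can start with no known liver or creatinine result from after Cycle 1 treatment, and Cycle 3 with none from after Cycle 2 treatment.

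Three features of Section 3.8 make this matter.

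- It states that acalabrutinib with R-ICE has had no phase I study, so chemistry after each cycle is direct safety evidence on the combination.
- Its non-hematologic rules depend on knowing the grade. A Grade 3 toxicity possibly or probably related to acalabrutinib calls for holding acalabrutinib and R-ICE, then resuming with a lower acalabrutinib dose. A Grade 4 toxicity attributed to acalabrutinib calls for stopping acalabrutinib and chemotherapy.
- It allows no modification of R-ICE, so holding the cycle is the main protection in the protocol text.

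A result read late still governs later doses, but it cannot undo doses already given.

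The lead-in is also affected. The DLT period closes just before Cycle 2 begins, and the Cycle 2 Day 1 panel is the only scheduled liver and creatinine test after Cycle 1 treatment starts. Footnote f allows that panel to be read, and on its wording even drawn, after the period has closed.

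**Working it through.** The plan gives no figure to reproduce. The check sets the provisions side by side, followed by schedule arithmetic.

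**Does any other provision supply the missing result?**

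| Provision | What triggers it | Gives a liver or creatinine result before the Cycle 2 or 3 dose? |
|---|---|---|
| Section 4, repeat laboratory tests within 48 hours before the next cycle | Patient is deteriorating | Not for a silent toxicity |
| Section 4, more frequent tests | Clinical indication | Not for a silent toxicity |
| Section 3.8: "In the event of severe renal toxicity or hepatotoxicity, laboratory tests may be repeated more frequently as necessary until the toxicity resolves" | Toxicity already known; optional | No |
| Section 3.8, day-21 actions and Grade 3/4 rules | Toxicity already known | No |
| Section 4.1.11, electrolyte panel | Unscheduled ECG | No; covers calcium, magnesium and potassium only |
| Footnote l, directed exam, potassium and urinalysis | None; every R-ICE day | No; results not tied to dosing |

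The provisions that could produce a liver or creatinine result are conditional. The unconditional one, footnote l, does not measure ALT, bilirubin or serum creatinine.

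**Does the meaning of study drug change the answer?** The synopsis lists five agents under that term. Sections 3.8 and 5.2.3 use it for acalabrutinib alone. On the first reading, footnote f also covers R-ICE. On the second, it covers acalabrutinib, and the protocol is silent on R-ICE beyond leaving it to institutional policy (Section 3.5.3). On either reading, nothing in the protocol requires chemistry results before R-ICE.

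**Schedule arithmetic**

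- Tests per cycle: hematology on Day 1, once in Days 7–10, and on Day 14 = 3; full chemistry on Day 1 = 1.
- Analytes listed in Section 4.1.11: 18. Repeated on schedule within the cycle: potassium only. 18 − 1 = 17 with no scheduled repeat.
- Interval between successive Day 1 visits: nominally 21 days. With the window in "Cycles 2 to 3 (Day 1, + 7 or - 3 days"), it is 21 − 3 = 18 to 21 + 7 = 28 days.
- Interval between panels with day-before sampling: shortest 18 − 1 = 17 days (first panel on Day 1, next the day before dosing); longest 28 + 1 = 29 days (first panel the day before, next on Day 1).
- From the Cycle 1 panel to the Cycle 2 panel when footnote k is used: up to 28 + 7 = 35 days.
- Cycle starts under the rule: Cycles 2 and 3, so 2 per patient. Stage 1: 20 × 2 = 40. Both stages: 46 × 2 = 92. These are upper bounds, reached only if every patient receives three cycles. They also assume that lead-in patients count within the 20 and 46, which the protocol does not state.

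The test counts and intervals show why the Day 1 panel carries so much weight. They do not measure how often harm would occur.

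**The case against.** The strongest reply is that there is no true contradiction. Footnote f says when a result is due; it does not waive Section 3.8. A site that starts a cycle with an unrecovered Grade 3 toxicity departs from Section 3.8 whatever the schedule allows, and a careful site satisfies both rules by waiting. R-ICE is left to institutional policy, as is the management of renal and hepatic reactions (Section 3.8), and those policies may well require chemistry before chemotherapy. All of this stands, and it limits the practical gap. It does not close it: the protocol then relies on site habit while its own schedule says that waiting is unnecessary.

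A second reply is that the dose at stake is small for acalabrutinib. It is taken about every 12 hours on Days 1–21 of each 21-day cycle, so without a delay the patient was already taking it the day before, and waiting for a local result might avert perhaps one dose. That is fair. The weight of the point falls on R-ICE, for which nothing in the protocol requires the result first.

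Third, daily potassium, urinalysis and examination on R-ICE days reduce the electrolyte and renal risk somewhat. They do, but they would not reveal a silent rise in liver tests or creatinine.

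Fourth, the scenario is narrow. The toxicity must be silent, Grade 3 or higher, first seen on Day 1, and judged clinically significant by the investigator, at a site that does not check first. The background is mildly reassuring: Section 1.2.2 reports 1% Grade 4 nephrotoxicity in the ICE group of the earlier randomized comparison, and Section 1.2.3 reports no DLTs among 21 patients given ibrutinib with R-ICE. Both are indirect, and neither gives the rate of silent Grade 3 chemistry on Day 1. As to clinical significance, Section 6.1.1 gives a value that requires withholding drug as an example, and that judgement cannot be made until the result is read.

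**Conclusion.** The concern holds. For Cycles 2 and 3 the schedule expressly permits dosing before the only scheduled full chemistry panel of the cycle is known, while Section 3.8 makes recovery from Grade 3 or higher non-hematologic toxicity a condition for starting. No other provision requires a liver or creatinine result before acalabrutinib or R-ICE. A toxicity already known is still caught, because Section 3.8 then makes the site check recovery. The gap is the silent toxicity first visible on Day 1.

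The size is two cycle starts per patient, at most 40 in stage 1 and 92 in total. These are opportunities, not events. The documents give neither the rate of silent Grade 3 or higher chemistry on Day 1 nor site practice, so no probability is offered. The point should be fixed because the correction is cheap and the consequence can be a full cycle of chemotherapy that Section 3.8 would have held. Confidence is medium because institutional policy, which the documents do not show, may already supply the missing step.

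**What to change.** Amend footnote f for Cycles 2 and 3 to require a pre-dose chemistry sample, on the dosing day or the day before, with results available before acalabrutinib or R-ICE is given. This applies footnote e's existing rule to chemistry, and naming both treatments removes the ambiguity over study drug. Cycle 1 can stay as it is, since the Section 3.8 conditions apply only after Cycle 1.

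The cost is one footnote by amendment, with no new blood sample and no extra panel. The downside is an occasional wait of some hours for a result. It should be small: both tests are run locally (Sections 4.1.10 and 4.1.11), the site already waits for hematology, and the sample may be drawn the day before.

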## Appendix 2. Performance Status Scores

ECOG Performance Status Scale		Karnofsky Performance Scale	
Grade	Descriptions	Percent	Description
0	Normal activity. Fully active, able to carry on all pre-disease performance without restriction.	100	Normal, no complaints, no evidence of disease.
		90	Able to carry on normal activity; minor signs or symptoms of disease.
1	Symptoms, but ambulatory. Restricted in physically strenuous activity, but ambulatory and able to carry out work of a light or sedentary nature (e.g., light housework, office work).	80	Normal activity with effort; some signs or symptoms of disease.
		70	Cares for self, unable to carry on normal activity or to do active work.
2	In bed <50% of the time. Ambulatory and capable of all self-care, but unable to carry out any work activities. Up and about more than 50% of waking hours.	60	Requires occasional assistance, but is able to care for most of his/her needs.
		50	Requires considerable assistance and frequent medical care.
3	In bed >50% of the time. Capable of only limited self-care, confined to bed or chair more than 50% of waking hours.	40	Disabled, requires special care and assistance.
		30	Severely disabled, hospitalization indicated. Death not imminent.
4	100% bedridden. Completely disabled. Cannot carry on any self-care. Totally confined to bed or chair.	20	Very sick, hospitalization indicated. Death not imminent.
		10	Moribund, fatal processes progressing rapidly.
5	Dead.	0	Dead.

**APPENDIX 3. KNOWN STRONG IN VIVO INHIBITORS OR INDUCERS OF CYP3A**

Strong Inhibitors of CYP3Aa	Strong Inducers of CYP3Ad
boceprevir	carbamazepine e
clarithromycin b	phenytoin e
conivaptin b	rifampin e
indinavir	St John's wort e
itraconazole b	
ketoconazole b	
lopinavir/ritonavir b (combination drug)	
mibepradil c	
nefazodone	
nelfinavir	
posaconazole	
ritonavir b	
saquinavir	
telaprevir	
telithromycin	
voriconazole	

- a. A strong inhibitor is defined as an inhibitor that increases the AUC of a substrate by  $\geq$  5-fold.
- b. In vivo inhibitor of P-glycoprotein.
- c. Withdrawn from the United States market because of safety reasons.
- d. A strong inducer is defined as an inducer that results in  $\geq$  80% decrease in the AUC of a substrate.
- e. In vivo inducer of P-glycoprotein.

Note: The list of drugs in these tables is not exhaustive. Any questions about drugs not on this list should be addressed to the Sponsor of the protocol.

Source:

FDA Drug Development and Drug Interactions: Table of Substrates, Inhibitors and Inducers . Web link Accessed 11 June 2015:  
<http://www.fda.gov/Drugs/DevelopmentApprovalProcess/DevelopmentResources/DrugInteractionsLabeling/ucm093664.htm#inVivo>

## Appendix 4. Adverse Event Assessment of Causality

Adverse Event: \_\_\_\_\_

Is there a reasonable possibility that the event may have been caused by study drug? No \_\_\_\_\_

Yes \_\_\_\_\_

The descriptions provided below will help guide the principal investigator in making the decision to choose either "yes" or "no":

No = There is no reasonable possibility that the event may have been caused by study drug.

The adverse event:

- may be judged to be due to extraneous causes such as disease or environment or toxic factors
- may be judged to be due to the subject's clinical state or other therapy being administered
- is not biologically plausible
- does not reappear or worsen when study drug is re-administered
- does not follow a temporal sequence from administration of study drug

Yes = There is a reasonable possibility that the event may have been caused by study drug.

The adverse event:

- follows a temporal sequence from administration of study drug
- is a known response to the study drug based on clinical or preclinical data
- could not be explained by the known characteristics of the subject's clinical state, environmental or toxic factors, or other therapy administered to the subject
- disappears or decreases upon cessation or reduction of dose of study drug
- reappears or worsens when study drug is re-administered

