**STUDY SYNOPSIS**

Study Title	A Phase 2, open-label study of acalabrutinib in combination with R-ICE for relapsed or refractory non-germinal center diffuse large B cell lymphoma, transformed chronic lymphocytic leukemia/small lymphocytic leukemia or transformed marginal zone lymphoma
Protocol Number	20190706
Study Drug	ACALABRUTINIB (ACP-196), rituximab, ifosfamide, etoposide, carboplatin
Phase	2
Coordinating and Study Center	Sylvester Comprehensive Cancer Center
Additional Study Centers	
 
• Moffitt Cancer Center
 
• City of Hope
 

Study Objectives	
Primary Objective
 
 
• Improve complete remission (CR) rate of R-ICE for rel/ref non-GC DLBCL and transformed histologies from 29% to 50% with acalabrutinib + R-ICE for 3 cycles by RECIL.
 
 
Secondary Objectives
 
 
• Safety and tolerability of acalabrutinib with R-ICE in patients with rel/ref DLBCL
 
• (partial remission) PR, CR, overall response rate (ORR) of acalabrutinib + R-ICE
 
• Ability to mobilize <math>\geq 2 \times 10^6</math> CD34+ cells/kg
 
• Event-free survival (EFS), progression-free survival (PFS) and overall-survival (OS) at 1 year
 
 
Exploratory Objective
 
 
• Correlate efficacy endpoints (ORR, PFS, OS) with: baseline metabolic tumor volume (MTV), circulating cell-free tumor DNA (ctDNA), and the results of next-generation sequencing (NGS) of tumor. NGS in diagnostic biopsy if available.
 

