#### Dose Limiting Toxicity: acalabrutinib + R-ICE

The DLT evaluation period begins with the first dose of acalabrutinib and ends immediately prior to the initiation of the second cycle. Only toxicities that occur during the DLT period will be used for the purposes of defining DLT. However, toxicities that occur in all cycles will be considered in the overall decisions of the investigators. The first 3-6 subjects will be evaluated for DLTs per above. Subjects considered non-evaluable for DLT may be replaced, but the safety profile of these subjects will be included in the investigator review. Subjects considered non-evaluable for DLT are subjects who do not complete Cycle 1 for reasons other than toxicity. Subjects who experience a DLT may continue treatment on the study at a lower dose of acalabrutinib.

The following will be considered DLTs after confirmation by the investigators:

- Complete treatment interruption of more than 7 days (28 days of the cycle) for acalabrutinib-RICE-related Grade  $\geq 2$  toxicities within Cycle 1

- Any Grade 3 or Grade 4 non-hematological toxicity that is at least possibly related to the study drugs
  - excluding:
    - Grade 3 nausea or vomiting responsive to anti-emetic treatment,
    - Grade 3 diarrhea responding to anti-diarrheal treatment,
    - Grade 3 fatigue/asthenia unless persisting for 7 days after stopping acalabrutinib and absent at baseline
    - alopecia
  - including:
    - persistent Grade  $\geq$  2 nausea and/or vomiting despite prolonged (more than 7 days continuously) anti-emetic treatment (5 HT3 antagonist, antihistamine, metoclopramide)
- Grade  $\geq$  2 hemorrhagic events requiring medical intervention
- Grade 4 hematological toxicity defined as:
  - Febrile neutropenia (ANC < 500 cells/ $\mu$ L with fever [body temperature  $\geq$  38.5°C] or sepsis) or Grade 4 neutropenia (ANC < 500 cells/ $\mu$ L) requiring at least 1 week delay of the next treatment cycle
  - Grade 4 thrombocytopenia (Platelet count < 25,000 cells/ $\mu$ L) requiring at least 1 week delay of next treatment cycle

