Based on the specific adverse event observed, 1 dose level reduction is permitted for acalabrutinib (see Table below). If acalabrutinib is withheld for  $\leq$  1 week due to acalabrutinib-related toxicity; study drug should be resumed with a dose reduction when treatment resumes following recovery from the toxicity. If there is unacceptable toxicity despite 1 dose reduction the treatment should be discontinued. If treatment must be withheld for an acalabrutinib-related adverse event that fails to resolve to an acceptable level (eg,  $\leq$  Grade 1 nonhematologic toxicity) within 1 week after the date acalabrutinib was withheld, treatment with acalabrutinib should be permanently discontinued. In this event, the subject will be discontinued from the treatment, and End-of-Treatment Visit assessments will be performed including through the protocol-specified AE reporting window and have follow-up for ongoing SAEs to resolution or stability unless the subject lost to follow-up. (see section 6.2.6)

Acalabrutinib dose adjustments also apply to cycle 1.

**Acalabrutinib** dose will not be reduced for hematological toxicities unless the hematologic toxicities fail to recover by day 21 of a cycle.

The actions in the table below should be taken for the following toxicities at day 21 of the cycle:

- Grade 4 ANC (<500/ $\mu$ L) for  $>7$  days
- Grade 3 thrombocytopenia (<50,000/mcL) in the presence of clinically significant bleeding events
- Grade 4 thrombocytopenia (<25,000/mcL)
- Grade 3 or 4 nausea, vomiting, or diarrhea, if persistent, despite optimal antiemetic and/or anti-diarrheal therapy
- Any other Grade 4 or unmanageable Grade 3 toxicity.

For Grade 3 or 4 atrial fibrillation or persistent atrial fibrillation of any grade, consider the risks and benefits of acalabrutinib treatment. *If clinically indicated, the use of anticoagulants or antiplatelet agents may be considered for the thromboprophylaxis of atrial fibrillation.*

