### **Non-hematological grade 3 or higher toxicities**

- For Grade 3 possible or probable acalabrutinib-related non-hematologic toxicities (other than the adverse events specifically described in this section), therapy (acalabrutinib and R-ICE) is to be held for a maximum of 1 week (and d28 of a cycle) until the toxicity returns to Grade 1 or less. If grade 2 during the first cycle, this will be considered a DLT.
- For any Grade 4 non-hematologic toxicity attributed to acalabrutinib, discontinue acalabrutinib and chemotherapy for all remaining cycles; subject is discontinued from study treatment and must complete protocol-specified AE reporting along with follow-up for ongoing SAEs to resolution unless the subject is lost to follow-up.
- If Grade 3 toxicity returns to Grade 1 or less by Day 28, then proceed with next cycle of therapy with acalabrutinib reduced to the next lower dose level.

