### **6.2.1 Adverse Event Reporting Period**

The AE reporting period for this study begins when the subject receives the first dose of study drug and ends 30 days after the last dose. An exception to this reporting period is any AE occurring due to a protocol-defined screening procedure. If any SAE occurs beyond 30 days after the last dose of acalabrutinib **AND** it is assessed by the investigator as related to acalabrutinib, it must be reported as an SAE.

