### **6.2.2 Assessment of Adverse Events**

Investigators will assess the occurrence of AEs and SAEs at all subject evaluation time points during the study. All AEs and SAEs whether volunteered by the subject, discovered by study personnel during questioning, or detected through physical examination, or other means, will be recorded in the subject's medical record and on the AE CRF.

Disease progression itself is not considered an AE; however, signs and symptoms of disease progression may be recorded as AEs or SAEs.

Each recorded AE or SAE will be described by its diagnostic term, duration (eg, start and end dates), severity, regulatory seriousness criteria, if applicable, suspected relationship to the study drug (see following guidance), and any actions taken. The relationship of AEs to the study drug will be assessed by means of the question: 'Is there a reasonable possibility that the event may have been caused by the study drug?' per FDA guidance on safety reporting requirements (FDA Guidance 2012).

See Appendix 4 for more detail on assessing relationship.

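### One yes/no causality question about an inconsistently used term, study drug, cannot yield both acalabrutinib-related and combination-related safety data

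*Combined protocol and SAP*

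**What the plan says.** Section 6.2.2 has the relationship of every adverse event judged by one question, "Is there a reasonable possibility that the event may have been caused by the study drug", and points to Appendix 4 for guidance. Appendix 4 repeats it, "Is there a reasonable possibility that the event may have been caused by study drug", and offers only Yes or No. Its guidance for No includes events put down to other treatment the subject is receiving. The SAE report described in 6.2.5.1 asks for a causal relationship without naming a drug or a scale.

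The term is used in two ways. The Study Drug row of the synopsis reads "ACALABRUTINIB (ACP-196), rituximab, ifosfamide, etoposide, carboplatin". Section 3.5.2 calls acalabrutinib the investigational product, and the dose-reduction text in 3.8 uses the singular term for acalabrutinib: "study drug should be resumed with a dose reduction when treatment resumes following recovery from the toxicity".

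The rules that use attribution differ in what they ask for:

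- Permanent discontinuation in 3.8: "If treatment must be withheld for an acalabrutinib-related adverse event that fails to resolve to an acceptable level".
- Holding treatment for Grade 3 events in 3.8: "For Grade 3 possible or probable acalabrutinib-related non-hematologic toxicities".
- A DLT criterion in 3.8: "Any Grade 3 or Grade 4 non-hematological toxicity that is at least possibly related to the study drugs".
- SAEs more than 30 days after the last dose (6.2.1): "assessed by the investigator as related to acalabrutinib, it must be reported as an SAE".
- SAEs in follow-up (Appendix 1, note n): related to study drug, with no drug named.

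**The concern.** The trial has one arm and adds acalabrutinib to R-ICE, a pairing that Section 3.8 says has not been studied in phase I. Section 1.5 describes hematologic toxicity with R-ICE as universal, with 57% of patients needing transfusion. With no control arm, investigator attribution is a main means of telling added toxicity from backbone toxicity, and Section 3.1.2 makes relationship to study drug a stated safety parameter.

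If three centers answer a question whose subject is not fixed, the same R-ICE toxicity can validly be Yes at one center and No at another. The related-event tables would then mix two meanings. An auditor could not recover from that field which attribution lay behind an action taken under 3.8 or a report made under 6.2.1. Attribution is also hard to reconstruct reliably once the trial is over.

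**Working it through.** No arithmetic applies and the plan states no figure to reproduce. The check sets each place that records or uses attribution beside the others, then asks whether one yes/no answer serves them all.

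| Place | Relation to what | Wording of the judgement |
|---|---|---|
| 6.2.2, Appendix 4 | study drug (singular) | yes/no, reasonable possibility |
| 6.2.5.1, SAE report | not stated | not stated |
| 3.8, withholding, reduction, permanent discontinuation | acalabrutinib | related |
| 3.8, Grade 3 non-hematologic | acalabrutinib | possible or probable |
| 3.8, Grade 4 non-hematologic | acalabrutinib | attributed |
| 3.8, DLT: treatment interruption | acalabrutinib with R-ICE | related |
| 3.8, DLT: Grade 3 or 4 non-hematologic | study drugs (plural) | at least possibly related |
| 3.8, DLT: hemorrhage, Grade 4 hematologic | no attribution condition | none |
| 6.2.1, late SAE | acalabrutinib | related |
| 6.2.6, expedited reporting | investigational product | attributable |
| Appendix 1, note n | study drug | related |

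**Reading A: the term means all five agents, as in the synopsis row.** A Yes says that at least one of the five may be the cause. It does not say whether acalabrutinib is among them. The attribution used by the acalabrutinib rows cannot be derived from it.

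**Reading B: the term means acalabrutinib, as in the dose-reduction text.** A Yes now matches the acalabrutinib rows. An event put down to R-ICE alone is No, and falls with events put down to disease or other causes. The attribution used by the two combination-based DLT rows cannot be derived from it.

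Appendix 4 does not settle the choice, because it does not say whether R-ICE counts as study drug or as the other therapy that points to No.

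**With two yes/no items**, one for acalabrutinib and one for R-ICE, each event falls in one of 2 × 2 = 4 cells. Acalabrutinib-related is read from the first item, R-ICE-related from the second, and combination-related is Yes on either. Both kinds of table can then be produced.

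**Two internal differences remain whatever the form looks like.** The late-SAE rule in 6.2.1 names acalabrutinib, while note n of Appendix 1 says study drug. The DLT list in 3.8 is combination-based where it uses attribution, but the acalabrutinib-related Grade 3 rule in the same section also contains a sentence classing a cycle 1 event as a DLT. DLT attribution therefore has two bases within 3.8.

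**The case against.** The best defense is that the body of the protocol mostly uses the singular term for acalabrutinib: the hepatic-impairment text in 3.8 and the compliance analysis in 5.2.3 do so, and the DLT criterion turns to the plural when it means the combination. The synopsis row is a listing of the regimen, not a definition. On that view Appendix 4 already fits the acalabrutinib rules. Much of this stands, but it is Reading B, which leaves relation to R-ICE unrecorded, and usage is not uniform enough to rely on.

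Two further objections stand in part. The words possible and probable are largely covered by a question about reasonable possibility, so that mismatch needs a sentence of explanation and not a graded scale. The CRF and its completion guidelines are not in the documents and may already ask more. Sections 6.2.2 and 6.2.5.1 also capture actions taken and changes to study drug. The point concerns what 6.2.2 and Appendix 4 prescribe.

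A reader might infer more: that the ambiguity pools two meanings in the DLT count and so could change the lead-in dose level. The documents do not support this. The listed DLT criteria either refer to the combination or carry no attribution condition, and DLTs are declared after confirmation by the investigators, not computed from the Appendix 4 answer. Any probability put on such an effect would rest on event rates that the documents do not give. Nor do all dose rules turn on acalabrutinib alone: some items in the day-21 action list in 3.8 require no attribution.

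**Conclusion.** The concern holds as a limitation of the safety data. As described, one yes/no answer cannot support both acalabrutinib-related and combination-related tables, nor show the attribution behind both sets of rules, whichever reading of the term is taken. The conclusion assumes that the AE form follows 6.2.2 and Appendix 4 and adds no separate item for R-ICE; if it does add one, what remains is the undefined term and the inconsistent wording.

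The size is modest and cannot be put in numbers from these documents. It bears on descriptive safety summaries and on auditability. The CR rate, its exact interval and the Simon decision rule do not depend on it.

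**What to change.** 1. Define study drug once, and use a different term for the combination.
2. In 6.2.2, Appendix 4 and the AE and SAE forms, replace the single question with two: related to acalabrutinib (yes/no) and related to R-ICE (yes/no). Reword the Appendix 4 guidance so that other therapy clearly means treatment outside the regimen.
3. State in Section 5 that adverse event tables will be given by both items.
4. Reconcile the attribution wording of the DLT list with that of the Grade 3 and Grade 4 rules in 3.8, and of 6.2.1 with note n of Appendix 1. Say how possible or probable, and attributed to, correspond to the recorded answer. Which attribution each clinical rule should use is for the sponsor and investigators to settle; none is proposed here.

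The cost is one extra CRF field, a little more investigator work per event, and wording changes in the sections named. For patients already entered, the second item would have to be completed from source records, so the change is best made early.
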